8.3.5. GO-QoL Questionnaire (Visual Function and Appearance Scale Scores)

Descriptive summaries of the transformed VF scale scores and transformed A scale scores and change from Study Baseline will be provided by treatment received in HZNP-TEP-301 for the ITT Population at Week 24. In addition, descriptive summaries of transformed VF and A scale scores will be provided by treatment received in HZNP-TEP-301 for the ITT Population for each visit in the Treatment Period and for HZNP-TEP-301 proptosis non-responders in the Follow-Up Period.

8.3.6. Investigator Assessment of Active Disease

Investigator assessment of active disease (active disease, inactive disease) will be collected on Day 1, Week 6, Week 12, Week 18, and Week 24 (or PW) during the Treatment Period, and for HZNP-TEP-301 proptosis non-responders at Week 28, Week 36 and Week 48 (or PW). Descriptive summaries of the observed results will be provided by treatment received in HZNP-TEP-301 for the ITT Population at Week 24.

In addition, descriptive summaries of results will be provided by treatment received in HZNP-TEP-301 for the ITT Population for each visit in the Treatment Period and for HZNP-TEP-301 proptosis non-responders in the Follow-Up Period.

9. ANALYSIS OF PHARMACOKINETICS

PK blood samples will be collected at pre-dose (within 1 hour prior to infusion) and the end of infusion at Day 1, Weeks 3 and 9, as well as single samples at Weeks 1, 4, and 24.

Length of infusion will be approximately 90 min for infusion 1 (Day 1) and 2 (Week 3) while 60 min for remaining doses. Pre-dose PK sampling will be considered as time 0 and the end of infusion time will be recorded.

The following presentations of subject serum concentration data covered in this SAP will be provided for teprotumumab for the PK Population:

- A listing including subject, week/time point (actual, planned), treatment and serum concentrations. Actual end of infusion sampling times are expressed relative to the start time of infusion.
- A table summary of serum concentrations at each time point (n, mean, SD, coefficient of variation (CV)% calculated as $100\% \times SD/\text{mean}$, minimum, 25th percentile, median, 75th percentile and maximum)

Concentrations below the limit of quantification (BLQ) collected on Day 1 pre-dose will be summarized as zero. All other concentrations BLQ will be excluded from the analysis summaries.

An additional analysis of PK is described in Section 10.4.

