**Study Design (continued):**

Treatment Period in Study HZNP-TEP-301 and are proptosis non-responders or were proptosis responders at Week 24 but meet the criteria for re-treatment due to relapse (see [Section 9.3.4](#)) during the Follow-Up Period of HZNP-TEP-301 will be eligible for enrollment. The study treatment previously administered in HZNP-TEP-301 (teprotumumab or placebo) will remain masked throughout this extension study.

All subjects who choose to participate will receive 8 infusions of teprotumumab (10 mg/kg for the first infusion followed by 20 mg/kg for the remaining 7 infusions) in an open-label fashion. The Baseline (Day 1) Visit of this extension study will occur within 14 days after the final visit of Study HZNP-TEP-301 (Week 24 for proptosis non-responders and up to Week 72 for subjects who relapse). During the open-label Treatment Period, study drug infusions are scheduled for Day 1 (Baseline), and Weeks 3, 6, 9, 12, 15, 18, and 21 (with a final visit at Week 24 of the 24-Week Treatment Period).

[figure not shown]
All study drug dosing will be performed at the clinic under the supervision of clinic staff, and at any scheduled infusion, the infusion rate may be reduced or the dose may be interrupted or held based on decreased tolerability (see [Section 9.4.6.3.2](#) for details). On each dosing day, scheduled assessments (except for adverse event [AE] and concomitant medication use monitoring, which will be monitored throughout the clinic visit) will be completed prior to study drug dosing. After each of the first 2 infusions, subjects will be contacted by phone/email the following day and will return to the clinic 1 week after the infusion (Weeks 1 and 4) for safety and tolerability assessments; additional phone/email contacts and clinic visits may also be conducted for any subject experiencing an infusion-associated event.

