TED01RV was the first study in which non-oncology subjects received teprotumumab. This study enrolled 87 subjects (43 teprotumumab; 44 placebo) between the ages of 18 and 75 years with recent onset ( $\leq$  9 months from diagnosis) moderate-to-severe active TED. The primary efficacy endpoint was the overall responder rate (decreases from Baseline of  $\geq$  2 points in overall Clinical Activity Score [CAS] and  $\geq$  2 mm in proptosis, provided that there was no deterioration [i.e., increases of  $\geq$  2 points in CAS or  $\geq$  2 mm in proptosis] in the non-study eye) at the end of the 24-week treatment phase. In this study, the responder rate was significantly greater with teprotumumab treatment compared to placebo (69% versus 20%;  $p < 0.001$ ) at Week 24. Therapeutic effects were rapid, with increased responder rates in the teprotumumab group relative to placebo detected at Weeks 6, 12, and 18 (all  $p < 0.001$ ). The secondary endpoints (QoL, proptosis, and CAS as continuous variables) all supported the primary analysis conclusion that teprotumumab was superior to placebo in the treatment of TED. Population PK modeling in TED01RV confirmed that trough concentrations were consistently above the 20 µg/mL threshold, which had been previously determined by Roche PK/PD modeling as resulting in > 90% IGF-1R occupancy in the tissues. Results of the TED01RV study were published in the New England Journal of Medicine [Smith et al, 2017].

Of the AESIs identified in the oncology studies (i.e., infusion-associated events, thrombocytopenia, hyperglycemia, and anemia), the only one that emerged in the initial trial in subjects with TED was hyperglycemia. Among subjects treated with teprotumumab, hyperglycemia was uniformly mild in non-diabetic subjects and adequately controlled by

adjusting standard anti-diabetic therapy in diabetic subjects. Importantly, hyperglycemia in all teprotumumab-treated subjects was at Baseline levels after the end of the Treatment Period.

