Increase in blood glucose is a known AE observed in previous clinical trials with teprotumumab and other IGF-1R antagonists and is known to respond to treatment. Since a referral for treatment of hyperglycemia may take some time, if the Investigator considers it appropriate to continue the subject in the study, the next scheduled infusion visit may be skipped to allow modified anti-diabetic treatment to show its activity and hyperglycemia to return to mild/moderate level before dosing. The subject would then be dosed at the next scheduled visit (i.e., 6 weeks after the previous infusion). Fasting blood glucose levels must return to mild/moderate severity before the next scheduled infusion. The above process of withholding a scheduled infusion will be permitted only twice during the study.

Any changes to the scheduled dosing interval (q3W) or adjustments in the infusion rate should be reported to the Sponsor/CRO.

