10.4. IMMUNOGENICITY

Serum samples will be collected prior to dose at Day 1, Weeks 3, 9, 24, 36 and 48 (or PW). If a subject tests positive for ADA after confirmatory and reactive titer testing, the sample will then be tested for neutralizing antibody (NAb). If the subject tests positive for NAb, he/she will be followed until levels either revert to Study Baseline or the subject's value decreases or remains stable.

Immunogenicity endpoints include:

- Incidence of ADA and NAb (out of positive ADA samples, if applicable) by visit and provided by treatment received in HZNP-TEP-301

The count and percent of subjects will also be provided by treatment received in HZNP-TEP-301 for the following:

- Overall positive ADA result, defined as at least one confirmed positive antibody
- Cumulative negative ADA result, defined as negative ADA results at all time points for a subject
- A negative ADA on HZNP-TEP-302 Day 1 and a positive result at any post-dose visit

Immunogenicity sampling times and results will be listed.

Further, the mean and CV% (calculated as $100\% \times SD/mean$) of pre-dose serum concentrations will be provided by visit in the subset of subjects who are confirmed ADA positive, NAb positive (if applicable) and ADA negative for each visit. This analysis will be provided for the PK Population.

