14.3.4.1.1.2.2	Hematology Laboratory Test Results Shift from HZN-001 Baseline	ITT
14.3.4.1.2.1.1	Summary and Change from Study Baseline in Chemistry Laboratory Test Results	ITT
14.3.4.1.2.1.2	Summary and Change from HZN-001 Baseline in Chemistry Laboratory Test Results	ITT
14.3.4.1.2.2.1	Chemistry Laboratory Test Results Shift from Study Baseline	ITT
14.3.4.1.2.2.2	Chemistry Laboratory Test Results Shift from HZN-001 Baseline	ITT

14.3.4.1.2.3.1	Glucose Shift from Study Baseline by CTCAE Grade	ITT
14.3.4.1.2.3.2	Glucose Shift from HZN-001 Baseline by CTCAE Grade	ITT
14.3.4.1.3.1	Summary and Change from Study Baseline in Urinalysis Continuous Laboratory Test Results	ITT
14.3.4.1.3.2	Summary and Change from HZN-001 Baseline in Urinalysis Continuous Laboratory Test Results	ITT
14.3.4.1.3.2	Categorical Urinalysis Laboratory Test Results	ITT
14.3.4.1.3.3.1	Urinalysis Test Results Shift from Study Baseline	ITT
14.3.4.1.3.3.2	Urinalysis Test Results Shift from HZN-001 Baseline	ITT
14.3.4.1.4.1.1	Summary and Change from Study Baseline in Thyroid Panel Laboratory Test Results	ITT
14.3.4.1.4.1.2	Summary and Change from HZN-001 Baseline in Thyroid Panel Laboratory Test Results	ITT
14.3.4.1.4.2.1	Thyroid Panel Laboratory Test Results Shift from Study Baseline	ITT
14.3.4.1.4.2.2	Thyroid Panel Laboratory Test Results Shift from HZN-001 Baseline	ITT
14.3.4.2.1	Summary and Change from Study Baseline in Vital Signs	ITT
14.3.4.2.2	Summary and Change from HZN-001 Baseline in Vital Signs	ITT
14.3.4.3.1.1	Summary and Change from Study Baseline in ECG Parameters	ITT
14.3.4.3.1.2	Summary and Change from HZN-001 Baseline in ECG Parameters	ITT
14.3.4.3.2.1	Overall ECG Shift from Study Baseline	ITT
14.3.4.3.2.2	Overall ECG Shift from HZN-001 Baseline	ITT
14.3.4.3.3	Categorical ECG Results	ITT
14.3.4.4.1.1	Physical Examination (Pretibial Myxedema) Shift from Study Baseline	ITT
14.3.4.4.1.2	Physical Examination (Pretibial Myxedema) Shift from HZN-001 Baseline	ITT
14.3.4.4.2.1	Ophthalmic Examination Shift from Study Baseline	ITT
14.3.4.4.2.2	Ophthalmic Examination Shift from HZN-001 Baseline	ITT
14.3.4.4.2.3	Ophthalmic Examination Loss of 2 Lines of Vision or More	ITT
14.3.4.4.3	Incidence of Anti-Drug Antibody	ITT
14.3.4.4.4	Summary of Serum Concentrations of HZN-001 (ng/mL) by Presence of Anti-Drug Antibody	PK
14.3.4.5.1.1	Extent of Exposure in HZNP-TEP-302	ITT
14.3.4.5.1.2	Extent of Exposure in HZNP-TEP-301 and HZNP-TEP-302 Combined	ITT

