18. INDEX OF LISTINGS

Listing Number	Title	Population
16.2.1	Subject Disposition	All Subjects
16.2.2.1	Masked Protocol Deviations	All Subjects
16.2.2.2	Unmasked Protocol Deviations	All Subjects
16.2.3.1	Inclusion/Exclusion Criteria - Description	
16.2.3.2	Inclusion/Exclusion Criteria Not Met	All Subjects
16.2.3.3	Analysis Populations	All Subjects
16.2.3.4.1	Subject Visits and Follow-Up Contact	All Subjects
16.2.3.4.2	Phone or Email Contact	All Subjects
16.2.4.1	Subject Demographics	All Subjects
16.2.4.2	Medical History	All Subjects
16.2.4.3	Substance Use	All Subjects
16.2.4.4	Prior and Concomitant Medications	All Subjects
16.2.4.5	Concomitant Procedures	All Subjects
16.2.4.6	Prior and Concomitant Thyroid Eye Disease Medications	All Subjects
16.2.4.7	Thyroid Eye Disease Surgery during Follow-Up Contact Period	All Subjects
16.2.4.8	Thyroid Eye Disease Orbital Radiation during Follow-Up Contact Period	All Subjects
16.2.4.9	Follow-Up Contact - Thyroid Eye Disease Treatments	All Subjects
16.2.5.1	Study Drug Administration	All Subjects
16.2.5.2	Study Drug Compliance	All Subjects
16.2.5.3	Study Drug Accountability	All Subjects
16.2.6.1.1	Proptosis Responder	All Subjects
16.2.6.1.2	Time to Proptosis Response	All Subjects
16.2.6.1.3	Sustained Proptosis Response in the Follow-Up Period	Week 24 Proptosis Responders
16.2.6.2.1	CAS and Proptosis Categorical Response	All Subjects
16.2.6.2.1.1	Sustained Overall Response in the Follow-Up Period	Week 24 Overall Responders
16.2.6.2.1.2	Sustained CAS Categorical Response in the Follow-Up Period	Week 24 CAS Categorical Responders
16.2.6.2.2	Clinical Activity Score	All Subjects
16.2.6.2.3	Diplopia Response	All Subjects

16.2.6.2.4.1	Clinical Measures of Severity Scores - Exophthalmos (Proptosis), Bases, Subjective Diplopia Score and Eye Muscle Involvement	All Subjects
16.2.6.2.4.2	Clinical Measures of Severity Scores - Lid Aperture, Eyelids and Conjunctival Inflammation	All Subjects
16.2.6.2.4.3	Clinical Measures of Severity Scores - Corneal and Optic Nerve Involvement	All Subjects
16.2.6.2.5.1	Graves' Ophthalmopathy Quality of Life Scale (GO-QoL) - Visual Functioning	All Subjects
16.2.6.2.5.2	Graves' Ophthalmopathy Quality of Life Scale (GO-QoL) - Appearance	All Subjects
16.2.6.2.5.3	Graves' Ophthalmopathy Quality of Life Scale (GO-QoL) - Overall	All Subjects
16.2.6.3	Investigator Assessment of Active Disease	All Subjects
16.2.6.4	Serum Concentrations of HZN-001	All Subjects
16.2.7.1	Adverse Events	All Subjects

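### The table of trough concentrations by ADA status drops BLQ values after Day 1, and the cumulative-negative ADA label needs no result after an extension dose (minor, descriptive outputs only)

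*SAP*

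**What the plan says.** **BLQ handling.** SAP 9 has two rules. For the first sample: "Concentrations below the limit of quantification (BLQ) collected on Day 1 pre-dose will be summarized as zero". For the rest: "All other concentrations BLQ will be excluded from the analysis summaries". It then names SAP 10.4 as a further PK analysis. There, the mean and CV% of "pre-dose serum concentrations will be provided by visit in the subset of subjects who are confirmed ADA positive", NAb positive or ADA negative. This is Table 14.3.4.4.4, "Summary of Serum Concentrations of HZN-001 (ng/mL) by Presence of Anti-Drug Antibody". SAP 10.4 gives no BLQ rule. Pre-infusion PK samples are taken on Day 1 and at Weeks 3 and 9, with single samples at Weeks 1, 4 and 24.

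**Cumulative negative.** SAP 10.4 counts a subject in this category when all of that subject's ADA results are negative. It sets no minimum number of results and does not ask for one after an extension dose. ADA is sampled on Day 1 and at Weeks 3, 9, 24, 36 and 48. It is not sampled when a subject withdraws during the Treatment Period (Protocol 9.5.6.11; SAP Table 1, footnote 21).

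**The concern.** The SAP 10.4 table is there to show whether exposure is lower in subjects with antibodies. A trough too low to quantify is the strongest form of that signal, and it is the value removed. The exclusion depends on the outcome and works in one direction: it raises the mean of whichever subgroup has BLQ troughs. Total loss of exposure in some subjects can then print a higher mean than a large partial loss. The PK Population does not prevent this. It needs only one quantifiable value at any time, so a subject with a measurable end-of-infusion sample stays in while the BLQ trough drops out.

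The cumulative-negative label has a related weakness. It reads as a statement about antibody formation, yet it can rest on a sample taken before any extension dose.

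**Working it through.** Neither document gives a limit of quantification, a BLQ rate, an ADA rate or a withdrawal rate, so there is no planned figure to reproduce. Every share and count below is an assumption.

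**Part A: which rule applies**

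1. SAP 9 applies its exclusion to the analysis summaries generally and calls 10.4 an additional PK analysis. SAP 10.4 does not override it.
2. The table therefore uses zero on Day 1 and exclusion at Weeks 3 and 9. Week 24 may also appear, because 10.4 loosely lists it among the pre-dose samples although no dose is given then.
3. Day 1 does not always follow a drug-free period: "The Baseline (Day 1) Visit of this extension study will occur within 14 days after the final visit of Study HZNP-TEP-301". For lead-in teprotumumab non-responders that final visit is Week 24. The same BLQ result in one subject is treated differently at Day 1 and Week 3.

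**Part A: size.** Let f be the BLQ share of a subgroup at one visit, M the mean of the quantifiable values and c their CV (40% assumed).

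- The printed mean is M; with BLQ as zero it is (1 − f)M. The ratio is 1/(1 − f): 1.00 at f = 0, 1/0.95 = 1.05 at 5%, and 1/0.90 = 1.11 at 10% (one subject in a subgroup of ten).
- Against half the limit, with the limit at 1% to 20% of M, the ratio is 1/((1 − f) + f·L/2), where L is the limit divided by M. At f = 10% this is 1/0.9005 = 1.11 to 1/0.910 = 1.10, so the choice between zero and half-limit matters little.
- The CV with BLQ as zero is √((c² + f)/(1 − f)) = √(0.26/0.90) = 53.7%, against a printed 40%.
- Partial against total loss, in the same 10% of subjects: a 90% fall that stays quantifiable prints 1 − 0.9 × 0.10 = 0.91 of the unaffected mean (CV 51.2%). A fall below the limit prints 1.00 (CV 40%), where zero would give 0.90 (CV 53.7%).

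**Part B: who can be labelled negative on Day 1 alone**

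1. The first ADA sample after an extension dose is at Week 3, before that visit's infusion.
2. A subject who stops before then has no withdrawal ADA sample.
3. Relapse subjects do not enter the Follow-Up Period (Protocol 9.3.3). Non-responders who stop dosing are only encouraged to continue (Schedule of Assessments footnote).
4. Without a Follow-Up sample, the Day 1 result is the only one, and it is negative at all of that subject's time points.
5. The default denominator in SAP 14.2.5.2 is subjects with an observation, so this subject stays in.
6. The ADA table uses the ITT Population, defined by consent. SAP 8.1 provides for ITT subjects who are never dosed, so an undosed subject with a negative Day 1 sample also qualifies.

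**Part B: size.** Take N = 20, p positive (all with post-dose results) and k negative on Day 1 only. As written, the negative share is (N − p)/N. Among subjects with a post-dose result it is (N − p − k)/(N − k). The difference is pk/(N(N − k)).

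| p | k | As written | Post-dose result required | Difference (points) |
|---|---|---|---|---|
| 1 | 1 | 19/20 = 95.0% | 18/19 = 94.7% | 0.3 |
| 2 | 2 | 18/20 = 90.0% | 16/18 = 88.9% | 1.1 (about 0.6 per subject) |
| 5 | 1 | 15/20 = 75.0% | 14/19 = 73.7% | 1.3 |

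If all rows keep the denominator of 20, each such subject moves 1/20 = 5.0 points from the negative row to a row of its own. That is visible relabelling, not a change in the rate among assessable subjects.

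**The case against.** **The rule may rarely matter.** Population PK modelling in the earlier TED study "confirmed that trough concentrations were consistently above the 20" µg/mL threshold, so BLQ troughs at Weeks 3 and 9 may be rare or absent. A low Week 9 value can also follow an infusion skipped for hyperglycemia (Protocol 9.4.6.3.2), with no antibody involved. This stands and limits the size.

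**The split has a rationale.** For lead-in placebo subjects a Day 1 BLQ value is a true zero, while a post-dose BLQ value is censored. That explains Day 1. It does not justify discarding censored low values from a comparison of low exposure.

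**Some of the missing information may be printed anyway.** SAP 6.1 summarizes continuous variables with n and median unless otherwise indicated. Whether naming only mean and CV% counts as otherwise indicated is unclear, and the table shells are in a separate file. Even if printed, n would not distinguish a BLQ exclusion from a missed sample. Individual values remain in Listing 16.2.6.4, "Serum Concentrations of HZN-001".

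**A new rule in 10.4 creates a mismatch with the main SAP 9 table.** True; a footnote is needed.

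**Part B is a corner case.** It needs a stop before Week 3 and no Follow-Up sample, or a subject never dosed, and SAP 12 expects the ITT and Safety Populations to be identical. ADA results are listed, so such a subject can be found. One could read all time points as every scheduled visit, but relapse subjects have no Week 36 or 48 visit and none could then qualify. Changing the negative denominator alone would also leave the positive and negative rows on different bases. That objection is sound and shapes the fix.

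**Conclusion.** Both parts hold as minor points about descriptive tables. As written, the SAP removes from the ADA/NAb exposure table the troughs that would show the greatest loss of exposure, and it allows a negative ADA label with no result after an extension dose. At an assumed 10% BLQ the printed mean is 1.11 times the mean with BLQ as zero; with no post-dose BLQ there is no effect. For the ADA label, the shift among assessable subjects is a fraction of a point to about one point per affected subject in an assumed group of 20. By-visit ADA incidence and the count of subjects negative on Day 1 and later positive are not affected, and neither is any efficacy endpoint.

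Three stronger readings are not supported:

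- **Large distortion.** A reader might apply the ratio to BLQ shares of 25% to 50%. Nothing in the documents suggests such shares, and the earlier trough evidence points the other way.
- **A spurious rise from Day 1 to Week 3.** This would require similar BLQ shares and similar quantifiable means at both visits. Lead-in placebo subjects have had no teprotumumab by Day 1, and relapse subjects enter as late as lead-in Week 72, so the visits differ because of dosing whatever the rule.
- **A real antibody effect is being hidden.** Only values below the limit are lost; low but quantifiable troughs stay in. Understatement occurs only if BLQ troughs are more frequent in antibody-positive subjects, which is not known. The separate vendor's PK analysis plan is also not available.

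**What to change.** **SAP 10.4, concentration table.** Summarize post-dose pre-infusion BLQ values as zero, as on Day 1. Print n and number BLQ by visit and ADA/NAb status, and confirm that the median is shown in line with SAP 6.1. State whether Week 24 belongs in the table. The SAP 9 rule can stay for the main concentration table, with a footnote on the difference or the number BLQ printed there too. Downside: a lower mean and larger CV wherever BLQ values occur.

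**SAP 10.4, ADA categories.** Require at least one ADA result after an extension dose for cumulative negative. Show subjects with no positive and no post-dose result as not evaluable. Present overall positive, cumulative negative and not evaluable on one common denominator. Downside: one extra row and a slightly smaller negative count.

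The cost is SAP wording and a few extra cells in two tables. No sample, visit or protocol change is needed.

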10. SAFETY

Safety analyses will be based on the ITT Population. Safety will be assessed on the basis of AEs, concomitant medication use (refer to Section 0), immunogenicity testing, physical examinations, ophthalmic examinations, vital signs, clinical safety laboratory evaluations, pregnancy tests, and ECGs. All safety information will be provided in subject listings.

10.1. EXTENT OF EXPOSURE

Study drug exposure will be measured as the number of study drug doses administered in HZNP-TEP-302 and HZNP-TEP-301/HZNP-TEP-302 combined (including any incomplete doses), the number of days on drug in HZNP-TEP-302 and HZNP-TEP-301/HZNP-TEP-302 combined, the total duration of treatment with HZN-001, and the number of days on study in HZNP-TEP-302. The number of doses administered will be summarized by treatment received in HZNP-TEP-301 and overall as the count and percentage of subjects receiving each number of doses, as well as a continuous variable. Further, the number of days on drug and on study will be summarized descriptively by treatment received in HZNP-TEP-301 and overall and calculated as follows:

- Number of days on drug in HZNP-TEP-302 = last dose date in HZNP-TEP-302 - first dose date in HZNP-TEP-302 + 1
- Total number of days on drug in HZNP-TEP-301/HZNP-TEP-302 combined:
 - For subjects receiving Placebo in HZNP-TEP-301 = Number of days on drug in HZNP-TEP-302
 - For subjects receiving HZN-001 in HZNP-TEP-301 = Number of days on drug in HZNP-TEP-302 + (last dose date in HZNP-TEP-301 - first dose date in HZNP-TEP-301) + 1
- Total duration of treatment with HZN-001 = last dose date in HZNP-TEP-302 - first dose date of HZN-001 (whether in HZNP-TEP-301 or HZNP-TEP-302) + 1
- Number of days on study in HZNP-TEP-302 (Treatment Period):
 - For subjects who discontinue during the Treatment Period = discontinuation date in HZNP-TEP-302 - first dose date in HZNP-TEP-302 + 1
 - For subjects who complete the Treatment Period = Week 24 visit date in HZNP-TEP-302 - first dose date in HZNP-TEP-302 + 1
- Number of days on study in HZNP-TEP-302 (Follow-Up Period):

- Subjects who do not enter the Follow-Up Period in HZNP-TEP-302 (i.e., discontinue study during the Treatment Period or complete the study at the end of the Treatment Period) will not contribute to this analysis
- For subjects who participate in the Follow-Up Period = Follow-Up Period completion/discontinuation date in HZNP-TEP-302 - Week 24 (or PW) visit date in HZNP-TEP-302 + 1
- Number of days on study in HZNP-TEP-302 (overall) = study discontinuation date/completion date in HZNP-TEP-302 (study visit completion/discontinuation) - first dose date in HZNP-TEP-302 + 1

A separate summary will also be provided by subject enrollment type (subjects who were proptosis non-responders in HZNP-TEP-301, subjects who relapsed during the Follow-Up Period in HZNP-TEP-301).

